Study visits and follow-up assessments will be scheduled as described above and we have many procedures in place to schedule and complete visits as planned (e.g., collection of contact information, reminder calls and cards, etc.). However, some flexibility is required to protect participants from unnecessarily limiting study procedures to a specific calendar day. If a participant misses an appointment, research staff will attempt to contact and reschedule, but we anticipate late and missed appointments.

**Training and therapists:** Treatment will be conducted by Drs. [name], [name], and a post-doctoral fellow. Training and supervision will consist of didactics, role plays and review of audiofiles of role-plays and actual sessions. Tapes will be rated for general skills and intended content by a modified Yale Adherence Competence Scale (YACS; Carroll et al., 2000). Therapists will begin treating patients once they score good or better on YACS items on role plays. Once recruitment begins, we will ask participants to consent for audiotaping, although they may participate in the study without taping (see Human subjects). If YACS item ratings on tapes fall below a mean of "good," additional training and supervision will occur. Drs. [name] and [name] have already met these adherence levels as part of a previous study using the same intervention. Any additional therapists will be trained and supervised by either [name] or [name].

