We will also compare proportions of subjects by group who are no longer gaming problematically, i.e., child reports no current DSM-5 IGD criteria and/or <5 criteria, and parent confirms no more problems for the most conservative approach. Logistic regressions will include important demographics and baseline indices of distress and severity of problems in Step 1. Step 2 will add treatment to determine if it adds unique variance in predicting outcomes after controlling for baseline indices.

**Power analyses.** This pilot is designed to assess feasibility, acceptability, and effect sizes. Thirty subjects per group are sufficient to address the former, to estimate effect sizes, and to detect moderately large differences of Cohen's (1988)  $d = 0.65$  with Type I error rate  $\alpha = .05$ , Type II error rate  $\beta = .20$ , and power  $[1 - \beta] = .80$ . If medium or larger effect sizes are noted, a larger randomized trial will be proposed to assess long-term efficacy.

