**Exploratory aims** are to evaluate potential mechanisms of actions of the intervention including: changes in number and location of gaming devices in the home, frequency of monitoring child's game playing (via self reports in both groups, and confirmed by completed logs in Group B), child's participation in alternate activities (ACC), and parental rewarding of child behaviors and family communications (PSSS, BFAM scores). Following recommendations of Morgenstern and Longabaugh (2000) for assessing mediation, Model 1 examines whether the treatments engender differential outcomes on gaming indices (i.e., Aim 2 above). Model 2 will test if potential mediators change differentially over time by condition. For these analyses, a composite indicator for each construct will be utilized (e.g., summary scores of number/location of gaming devices, monitoring frequencies, ACC, PSS and BFAM scores). Model 3 will examine partial correlations between post-treatment scores on these indices and gaming outcomes, after controlling for baseline scores. If these three models show significant effects, the final model will assess associations between these variables and gaming outcomes. Step 1 of this model will include baseline scores of the potential mediator(s). In step 2, treatment group will be entered, and in step 3, post-treatment scores of the mediator(s) will be included, and resulting predictive power of treatment condition examined. If treatment is no longer significant and the post-treatment mediation term is significant, criteria for full mediation are met. Although we do not expect to find full mediation with this sample size, potential mediators with medium or higher effect sizes in Models 2-3 will be considered for future evaluation and inclusion in this intervention, if main effects of treatment are noted (Aim 2).

We will also assess effect sizes on secondary outcomes, e.g., substance use, psychosocial functioning and symptoms, sleep, and quality of life. HLM, outlined above, will compare groups over time on these indices.

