## 2. ADEQUACY OF PROTECTION AGAINST RISKS

### a. Recruitment and Informed Consent.

Informed Consent: A trained research staff member (Bachelors level or above), under supervision of the PI, will obtain informed consent. All potential subjects will receive an explanation of this study protocol, its potential risks and benefits, and alternative treatment available. Following resolution of any questions, parents/guardians and adult children (i.e., age 18) who agree to participate will be asked to sign the study

consent form and HIPAA document. A signed copy of the consent and HIPAA form will be given to each participant. Assent will be obtained from children under the age of 18, and both child and parent must agree to participate prior to collection of study data or randomization to a condition. As noted above, individuals who choose not to participate or who are deemed ineligible will be referred for other services as indicated.

An audiotaping section within the consent form will be utilized for recording of interactions between research staff and study patients, including baseline and follow-up interviews and therapy sessions. These audiofiles are utilized only for quality control procedures, to rate staff according to set standards in interview and treatment administration. Patients may participate in the study even if they do not choose to allow audiotaping (in our prior and ongoing studies, less than 5% of patients refuse audiotaping, and in this case both child and parent must agree or taping will not occur). The audiotaping consent section will explain that the purpose is to rate the staff member's interviewing and treatment administration skills.

b. Protection Against Risks. The following will protect against potential risks:

- i. Random group assignment is used, and about half of families will be assigned to the referral alone condition and half to the referral plus brief family behavioral therapy condition. These proportions will be outlined in the informed consent form, and patients will be made aware that they have about a 50% chance of being assigned to the family behavioral therapy condition. Patients may voluntarily end study participation if they are dissatisfied with their assignment.
- ii. The interviews and sample collections are brief, patients may skip questions or take a break if uncomfortable, and the particular instruments chosen are intended to minimize discomfort.

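### The final mediation model is fitted only after three significant tests, one of them the overall treatment effect, so at medium effects a true mediator would reach it in under half of trials, and no ungated indirect effect is planned

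*Combined protocol and SAP*

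**What the plan says.** The exploratory aims under Data analysis, repeated in item 10 of the Data and Safety Monitoring Plan, set out a stepwise mediation analysis.

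- Model 1 is the Aim 2 comparison: "Model 1 examines whether the treatments engender differential outcomes on gaming indices (i.e., Aim 2 above").
- Model 2 takes the mediators: "Model 2 will test if potential mediators change differentially over time by condition".
- Model 3 is a partial correlation between post-treatment mediator scores and gaming outcomes. It controls for baseline scores; treatment is not named as a control.
- The final model enters baseline mediator scores, then treatment, then post-treatment mediator scores. Its entry condition is: "If these three models show significant effects, the final model will assess associations between these variables and gaming outcomes".

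The plan then concedes that full mediation is not expected with this sample. It adds a second route: mediators with at least medium effects in Models 2 and 3 will be considered for later work, but only "if main effects of treatment are noted (Aim 2"). What counts as noted is not defined. No indirect effect and no interval for one is mentioned.

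**The concern.** An indirect effect can exist, and can be estimated, without a significant total effect. When much of a treatment's effect runs through one mediator, the test of the total effect can be the weakest of the three. Making it a condition of entry discards information on the mediator.

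The mediator-to-gaming path that mediation needs is the one with treatment held fixed. Model 3 as written does not give it, because treatment moving both variables would by itself produce a correlation. That path is estimated only in the last step of the gated model.

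At stake is a stated purpose of the pilot. Specific aims and Future directions both say that identified mechanisms will shape the next version of the intervention. The trigger for a larger trial is a medium or larger effect size, not a p-value. The pilot could therefore lead to the next trial while the mediation model meant to inform it is withheld.

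**Working it through.** **Inputs from the documents.** 30 per group, d = 0.65, alpha .05 and power .80 (Power analyses). Allocation is about equal: "about half of families will be assigned to the referral alone condition and half to the referral plus brief family behavioral therapy condition".

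**Assumptions.** The documents give no mediator path sizes, mediated shares, alpha for the mediation models, sidedness or dropout figure. I use alpha .05 two-sided with all 60 families analysed, then vary these.

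**Step 1: the plan's own figure.** This is the power of Model 1. The noncentrality is d·√(n/2) = 0.65 × √15 = 2.517.

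- One-sided: Φ(2.517 − 1.645) = 0.809 (0.800 with the t distribution). The stated 80% reproduces.
- Two-sided, unadjusted: Φ(2.517 − 1.960) = 0.711 (0.697 with t).
- Two-sided at d = 0.5: 0.5 × √15 = 1.936, giving 0.48 with t. Because all three tests must succeed, this alone caps the gate at about 48%.

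**Step 2: simulation model.** G is treatment (0/1) and baseline is taken as already partialled out. M = a·G + e and Y = c·G + b·M + e′, with the within-arm SD of M and of Y equal to 1. Total effect d = c + a·b.

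- Gate: p < .05 for Y on G, for M on G, and for the correlation of M with Y not adjusted for G.
- Joint test: p < .05 for M on G and for Y on M given G, with no requirement on Model 1.

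**Step 3: results, 30 per arm, two-sided.**

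| a | b | c | Total d = c + a·b | Gate | Joint test |
|---|---|---|---|---|---|
| 0.5 | 0.5 | 0.25 | 0.50 (half mediated) | 30% | 46% |
| 0.8 | 0.625 | 0 | 0.50 (all mediated) | 46% | 85% |
| 0.65 | 0.5 | 0.325 | 0.65 (half mediated) | 54% | 68% |
| 0.8 | 0.5 | 0.4 | 0.80 (half mediated) | 77% | 85% |
| 0.65 | 0.5 | 0 | 0.33 (all mediated) | 21% | 68% |
| 0.5 | 0.4 | 0 | 0.20 (all mediated) | 9% | 43% |

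Repeat runs agree to within about two percentage points. In the last two rows Model 1 alone has power of only about 24% (Φ(0.325 × √15 − 1.960) = Φ(−0.70)) and 12% (Φ(0.2 × √15 − 1.960) = Φ(−1.19)).

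**Step 4: sensitivity of the gate, half mediated, a equal to total d.**

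- One-sided tests: 44% at 0.5, 69% at 0.65, 87% at 0.8.
- 25 analysed per arm (the plan gives no rate, "but we anticipate late and missed appointments"): 25%, 45% and 68%.

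**Step 5: a smaller mediated share (30%), two-sided, 30 per arm.** Gate against joint test is 24% against 30% at 0.5, 47% against 45% at 0.65, and 71% against 55% at 0.8. In the last two cases the gate opens more often than the joint test succeeds, because the Model 3 correlation without treatment picks up treatment's effect on both variables. The gate is therefore not only strict; its third test measures the wrong path.

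**Step 6: the effect-size route.** I assume cut-offs of a standardised effect of at least 0.5 in Model 2 and a correlation of at least 0.3 in Model 3. Half mediated, they are met in 50% of trials at 0.5/0.5 (total effect/effect on the mediator) and 71% at 0.65/0.65. Requiring a main effect as well lowers this to 32–34% and 56–57%, whether that means Model 1 significant or an observed d of at least 0.5.

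**The case against.** A reader might infer that a real mediator would hardly ever be examined, or that the trial would yield nothing on mechanisms. The documents do not support either reading. Models 2 and 3 have no precondition, so the effect of treatment on each mediator and the baseline-adjusted correlation with gaming are obtained whatever Model 1 shows. The second route does not require significance in Models 2 and 3. At the effect the trial was sized for, the gate opens about half the time two-sided, and more often one-sided. The 21% and 9% figures belong to total effects of about 0.33 and 0.20, below the medium effect that the plan wants before a larger trial.

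It can also be said that the plan follows a published stepwise approach, calls the aim exploratory and disclaims full mediation at this sample size. Wanting some treatment effect before building on a mediator is a defensible development rule. An ungated analysis does not create power either: the joint test reaches only about 46% in the first row of the table.

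All of this limits the size of the point. It does not remove it. The disclaimer concerns how the final model would be read, not whether it is fitted. The second route still depends on an undefined main effect. Nothing fitted outside the gate gives the mediator path adjusted for treatment, or an indirect effect with its uncertainty.

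**Conclusion.** The concern holds in a limited form and is a minor one. The final mediation step depends on three significant results including the total effect, and it is the only place where the treatment-adjusted mediator path is estimated. With 30 per arm, two-sided 5% and at least half of the effect mediated, a true mediator reaches that step in under half of trials at d = 0.5, about half at d = 0.65 and about three-quarters at d = 0.8. The Model 1 requirement costs most when the total effect is modest and the mediator strong (46% against 85%).

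These rates rest on assumed path sizes, mediated shares and alpha, and on no dropout. Dropout lowers them and one-sided testing raises them. The structural point, that no ungated indirect effect is planned, rests on the text alone.

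**What to change.** In both places where the analysis is described, remove the requirement that all three models be significant. For each named mediator, estimate the indirect effect as the treatment-to-mediator path times the mediator-to-gaming path, with baseline scores and treatment in the outcome model. Give a bootstrap 95% interval, resampling families, whatever the Model 1 p-value. Report every named mediator and label the results exploratory. If the effect-size route is kept, define what counts as a main effect being noted.

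No new data are needed; the cost is revised wording and a short bootstrap per mediator. The drawback is wide intervals for several mediators. With a = 0.65 and b = 0.5, the approximate standard errors are √(2/30) = 0.258 for a and √0.75/√58 = 0.114 for b. The indirect effect is 0.65 × 0.5 = 0.325, with standard error √(0.5² × 0.258² + 0.65² × 0.114²) ≈ 0.149. The 95% interval is therefore roughly 0.325 ± 0.29. That is imprecise, but it shows openly what 60 families can say.

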Both parents may participate and will complete the parental assessments (est. 2 hours), and both (when available) can participate in the therapy, consistent with how family therapy is typically provided. Both parents and children will complete a therapy satisfaction form post treatment. Children and parents will receive \$30 in gift cards for completing the baseline assessment and the 4 week follow-up and \$50 in gift cards for the post-treatment and 24 week follow-up interviews (up to \$160/family member).

Family members may complete their follow-up measures through the survey function of REDCap in advance of their in-person meetings. When the research assistant calls to schedule the follow-ups, participants will be given the option of receiving the survey link through e-mail, receiving a paper copy of the assessments by mail, or completing the measures when they arrive for their in-person meeting. The week 4 assessment can be completed in its entirety by the participant at home through REDCap or the mail, unless the participant prefers an in-person meeting. Study visits may be completed over the phone if needed.

Parents will provide:

- basic demographics, including age, SES, gender, and education of parents and child, and indices of the child's school functioning: grades, tardiness, absences and disciplinary issues

- modified Treatment Service Review (TSR; McLellan et al., 1992) questionnaire about histories and current treatments received (of the child). Additional questions specific to treatment for video game addiction treatment will be administered at all time points.
- Parents will provide data about their own psychological symptoms (Brief Symptom Inventory [BSI]; Derogatis, 1992)
- emotional regulation (Difficulties in Emotion Regulation Scale [DERS]; Gratz & Roemer, 2004).
- Parents' perceptions of their child's gaming will be evaluated by a revised VGDS (Rehbein et al., 2015), which includes items about types and locations of all gaming devices in the home and frequencies with which they monitor their child's gaming behaviors.
- a semi-structured clinical interview using DSM-5 criteria (SCID; Petry et al., 2014), assessed over past year and past 2 months at BL and past 2 months at other time points.
- Parents will complete a TimeLine Follow-Back (TLFB; Sobell & Sobell, 1990) of the child's gaming, time spent watching others play online (e.g., YouTube, Twitch), and sleep

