Aim 1: To evaluate the feasibility and acceptability of this intervention, the proportion assigned to the intervention who complete all 6 sessions will be examined, as will parent and child ratings of satisfaction.

Aim 2: To examine the effect size of the intervention on reducing game playing days and durations of play, we will analyze TLFB data collected at each assessment period, with the greater report of parent or child used for each day. Hierachial linear models (HLM; Gibbons et al., 1993; Raudenbush & Byrk, 2002) will compare differences between groups over time. HLM is specifically designed for repeated measures designs with missing data, allowing for intra-subject serial correlation and unequal variance and covariance structures over time by incorporating available trend data for each individual with information on the group from which the subject is drawn. Maximum likelihood estimation enables analyses to be performed for the full trial without having to drop subjects with incomplete data, and both continuous and dichotomous variables can be analyzed. The model will include factors representing group, time, and their interaction, along with any important covariates.

We will also compare proportions of subjects by group who are no longer gaming problematically, i.e., child reports no current DSM-5 IGD criteria and/or <5 criteria, and parent confirms no more problems for the most conservative approach. Logistic regressions will include important demographics and baseline indices of distress and severity of problems in Step 1. Step 2 will add treatment to determine if it adds unique variance in predicting outcomes after controlling for baseline indices. See section 4 above for power analysis.

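### The full-mediation rule treats a non-significant treatment term as if no direct effect remained, which 30 families per group cannot show

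*Combined protocol and SAP*

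**What the plan says.** The exploratory aims (Data analysis, repeated in the Data and Safety Monitoring Plan, item 10) set out four models.

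- Model 1 is the Aim 2 comparison of gaming outcomes between groups.
- Model 2 asks whether each candidate mediator changes differently by group.
- Model 3 relates mediator to outcome: "Model 3 will examine partial correlations between post-treatment scores on these indices and gaming outcomes, after controlling for baseline scores".
- The final model runs only if Models 1 to 3 are all significant. It enters baseline mediator scores, then treatment group, then post-treatment mediator scores.

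The conclusion is then drawn by this rule: "If treatment is no longer significant and the post-treatment mediation term is significant, criteria for full mediation are met". The mediation text asks for no estimate or interval for the direct or indirect effect, and gives no margin below which a direct effect would count as negligible.

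The plan adds a caveat, "Although we do not expect to find full mediation with this sample size". It also says that, given an Aim 2 main effect, "potential mediators with medium or higher effect sizes in Models 2-3 will be considered for future evaluation and inclusion in this intervention". The sample size paragraphs (Power analyses; Monitoring Plan item 4) give 30 per group, d = 0.65, alpha .05 and power .80. No figure is given for the mediation analysis.

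**The concern.** The rule turns absence of evidence into a positive finding. A direct effect is only part of the total effect. It is also estimated less precisely, because treatment group and post-treatment mediator are correlated once therapy moves the mediator. A trial sized for the total effect will therefore often miss a real direct effect. If the mediator term is significant, the plan then calls the result full mediation.

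At stake is the report of the first randomised trial in this area. It could state that therapy works entirely through, say, parental monitoring when half of the effect came by another route.

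A second, smaller matter lies in Model 3, which names baseline scores as controls and does not mention treatment group. If group is left out, a mediator that therapy changes but that has no influence on gaming still correlates with gaming, because both follow group. The carry-forward sentence rests on Models 2 and 3 and does not require the final model, where group does appear.

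**Working it through.** **Plan's own figure.** With n = 30 per group and d = 0.65, the noncentrality is 0.65 × √(30/2) = 2.52. Power from the t distribution is 0.80 at one-sided .05 and 0.70 at two-sided .05. The plan does not state sidedness, which is a separate matter. On either reading the power is for the total effect.

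**Inputs.** From the plan: 60 families, 1:1, d = 0.65, alpha .05 (taken as two-sided below), and the rule and model sequence. Assumed, because the documents give no values: mediator shift a = 0.8, 1.2 or 1.6 SD; baseline-to-post correlation of the mediator 0.5; within-group SD of 1 for mediator and outcome; one mediator, one post-treatment outcome, no dropout, ordinary regression in place of HLM.

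**Power for the direct effect when half the effect is direct.** The direct effect is 0.65 × 0.5 = 0.325 SD. The mediator's effect on gaming is b = 0.325/a. In the final model:

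- residual variance = 1 − b²
- variance inflation V = 1/(1 − R²), with R² = 0.25a²/(0.75 + 0.25a²)
- SE = √[(1 − b²) × V/15], where 15 = 60 × 0.25

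| a | b | 1 − b² | V | SE | 0.325/SE | Power |
|---|---|---|---|---|---|---|
| 0.8 | 0.406 | 0.835 | 1.213 | 0.260 | 1.25 | 23% |
| 1.2 | 0.271 | 0.927 | 1.480 | 0.302 | 1.07 | 18% |
| 1.6 | 0.203 | 0.959 | 1.853 | 0.344 | 0.94 | 15% |

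**How often the rule declares full mediation.** Simulation, 20,000 trials per setting. The final model is reached if Models 1 to 3 each give p < .05. Full mediation is declared if group has p ≥ .05 and mediator p < .05. Half the effect is truly direct.

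| a | Reach final model | Declared full, of those | Of all trials |
|---|---|---|---|
| 0.8 | 65.4% | 61% | 40% |
| 1.2 | 63.5% | 43% | 27% |
| 1.6 | 61.1% | 29% | 18% |

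The last column is the product of the two before it, for example 0.654 × 0.611 = 0.400.

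**Is the label informative at all?** At a = 0.8, among trials reaching the final model, it appears in 96% when mediation is full, 61% when half the effect is direct, 26% when three quarters is direct, and 8% when the mediator is inert. It detects a mostly direct effect but separates full from half mediation poorly.

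**Secondary check, Model 3.** The screen is taken as a significant main effect, Model 2 d ≥ 0.5 and partial r ≥ 0.3. These cut-offs are assumed because the plan does not define medium.

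| a | Inert mediator passes, group omitted | Inert, group included | Half-mediator passes, group omitted | Half-mediator, group included |
|---|---|---|---|---|
| 0.5 | 3% | under 1% | – | – |
| 0.8 | 8% | about 1% | 62% | 45% |
| 1.2 | 16% | about 1% | 57% | 22% |
| 1.6 | 23% | about 1% | 54% | 12% |

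**The case against.** The best defence is that this is an exploratory aim of a Stage 1 pilot, that the rule is a conventional stepwise one, and that the authors doubt they will meet it. Carry-forward does not use the label, so no decision turns on it. All of that stands, and it limits the weight of the point. It does not rescue the rule. The caveat treats the small sample as making the criteria harder to meet, but half of the criteria is a non-significant treatment term, which a small sample makes easier to meet. The simulation includes the other half, a significant mediator term.

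On Model 3, a sensitive screen is defensible at this stage. Adding group costs real sensitivity, the carry-forward wording commits only to consideration, and it needs an Aim 2 main effect. The mediator shifts of 0.8 SD and above exceed the plan's only effect size; at 0.5 SD the false-pass rate is only 3%. These points stand, and they are why Model 3 is a note here and not the main finding. The main-effect condition does not protect, however: a treatment effect on gaming together with one on the mediator is what produces the spurious correlation.

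A reader might infer three stronger things that the documents do not support.

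- That Model 3 omits treatment group. The text neither names nor excludes it; the adjustment set is simply incomplete.
- That the label is worthless. It is rare when most of the effect is direct.
- That the error touches the Aim 2 comparison or the decision to propose a larger trial. Neither uses the rule.

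**Conclusion.** The rule is wrong as written. With d = 0.65, 30 per group and half of the effect direct, it would declare full mediation in about 61%, 43% or 29% of trials reaching the final model, at assumed mediator shifts of 0.8, 1.2 or 1.6 SD. The percentages depend on those shifts and on the simplified model. The direction does not: a non-significant term tested at 15% to 23% power cannot show that the effect is absent. The consequence is confined to how an exploratory result is reported, so this is a change worth considering rather than a threat to the trial.

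The Model 3 point holds only if group is left out. It is small for modest mediator shifts and grows with larger ones.

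**What to change.** In Data analysis (Exploratory aims) and Monitoring Plan item 10:

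1. Delete the full-mediation sentence. Report the indirect effect (treatment-to-mediator coefficient times mediator-to-outcome coefficient) and the direct effect, each with a bootstrap 95% confidence interval.
2. State that both estimates assume no unmeasured confounding of mediator and outcome. Mediators are not randomised, and the same informants supply both sides. Monitoring is measured "via self reports in both groups, and confirmed by completed logs in Group B", while gaming is scored "with the greater report of parent or child used for each day".
3. As a secondary clarification, report the group-adjusted Model 3 value (or the final-model mediator coefficient) beside the unadjusted one. State in advance which of them governs carry-forward and what counts as a medium effect.

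No new data are needed, only wording and slightly more analysis. The intervals will be wide. For a half-mediator the median limits are 0.06 to 0.63 SD (indirect) and −0.18 to 0.82 SD (direct) at a 0.8 SD shift, and −0.14 to 0.81 and −0.35 to 1.00 at 1.6 SD. That width is an honest picture of what 60 families can show. If the group-adjusted value governs, the screen loses the sensitivity shown in the last table, which is why both values should be shown.

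The change does not remove confounding. With an assumed residual mediator–outcome correlation of 0.2, the bootstrap interval for the indirect effect of an inert mediator (0.8 SD shift) wrongly excludes zero in about 32% of trials.
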